6.1.2 Screening/Washout Phase

Prior to performance of any trial related procedure (including washout), signed informed consent must be obtained from the subject.

A washout period will have to be completed for subjects who are or have recently been treated with anti-psoriatic treatments or other relevant medication not permitted as defined by the exclusion criteria (see Section [7.3](#)). The washout is to ensure that no other treatment could interfere with the response obtained with the IPs in the trial. The duration of the washout period is limited for logistical reasons to a maximum of 4 weeks. Because the maximum washout is 4 weeks, subjects who have recently been treated with biologics that require more than a 4 week washout period (e.g. ustekinumab should not be used for 16 weeks prior to commencing the trial), will not be eligible for the trial unless they have been off-treatment for several weeks (e.g. at least 12 weeks for ustekinumab) prior to the eligibility evaluation.

Assessment of subject eligibility should be made at a Screening Visit, prior to commencing a washout period. Screening assessments and trial procedures to be performed at Screening Visit are outlined in Section 8. On completion of the washout period, confirmation of the subject's ongoing eligibility for the trial will be made at Visit 1.

However, if no washout is needed the subject can enter Visit 1 directly.

6.1.3 Initial open-label treatment phase

Eligible subjects will first enter an initial open-label treatment phase, where they will be instructed to apply LEO 90100 once daily on the psoriatic lesions on trunk and limbs for 4 weeks. All trial medication needed for 4 weeks (7 cans of LEO 90100) will be dispensed at Visit 1.

The first application of the trial medication should be made at Visit 1 under the supervision and instruction of the trial staff or at home on the same day the subject attended Visit 1. For detailed treatment instructions, see section 10.2.

After 4 weeks, subjects will be asked to return to the trial site for clinical evaluation and medication accountability (Visit 2). All trial medication dispensed at Visit 1 will be collected.

Subjects who achieve treatment success (PGA score of 'clear' or 'almost clear' with at least a 2-grade improvement from baseline) at Visit 2 will be randomised in a ratio of 1:1 in a double-blind fashion to either LEO 90100 or vehicle (maintenance IP) twice weekly for 52 weeks.

The randomisation of subjects will be stratified by trial site, HPA axis testing, and by baseline disease severity, as determined by the PGA at Visit 1.

Randomised subjects will receive the supply of maintenance IP for 4 weeks and will be instructed on how to apply it during the maintenance phase and what to do in case of relapse.

Subjects who do not achieve treatment success after this initial open-label treatment phase will exit the trial.

6.1.4 Maintenance phase

During the maintenance phase, subjects will apply the randomised maintenance IP twice weekly on trunk and limbs to the areas where lesions have cleared or almost cleared after treatment was initiated at baseline. Any additional non-active psoriatic lesions (i.e. lesions not present at baseline that have been cleared or almost cleared by rescue treatment during a

relapse) should be treated with maintenance IP as well. Maintenance IP should be applied 3 or 4 days apart. The choice of the application days will be left to subjects' preference, and these days will be fixed throughout the trial (e.g., Thursday and Sunday); this needs to be settled at Visit 2. Subjects will be assessed by the investigator at the trial site every 4 weeks from Visit 2 to Visit 15. Furthermore, depending on when relapse occurs in relation to the regular 4-week visits (also referred to as 'scheduled' visits), additional (unscheduled) visits may be needed (outlined below).

All regular 4-week (scheduled) visits between or after an unscheduled visit or relapse follow-up visit should be performed.

Based on these rules, there are the following options:

6.1.4.1 Relapse at a regular 4-week (scheduled) visit

[figure not shown]
In case a relapse of psoriasis (defined as PGA of at least 'mild') is observed by the investigator at a regular monthly visit, the subject will be provided with rescue IP and instructed to apply it on the affected areas on trunk and limbs once daily for 4 weeks (all active psoriatic lesions including any new areas that become active during this 4-week treatment period).

Twice weekly maintenance treatment will continue unchanged on areas that are not active.

The subject will return to the trial site 4 weeks later to attend the regular monthly visit, where, if the subject is 'clear' or 'almost clear' according to PGA, maintenance treatment will be resumed on those areas. If the PGA of 'clear' or 'almost clear' is not achieved after 4 weeks of rescue treatment, the subject will exit the trial. For illustration, see Figure 2 below.

Figure 2 Relapse at a regular 4-week (scheduled) visit

6.1.4.2 Relapse between regular 4-week (scheduled) visits – more than one week prior to the next regular visit

If, in the opinion of the subject, a relapse of psoriasis occurs between regular visits when there is more than one week (7 days) to the next planned visit, the subject will contact the trial site to be assessed by the investigator at an unscheduled visit.

If relapse is confirmed by the investigator, the subject will be provided with rescue IP and instructed to apply it once daily for 4 weeks on any active psoriatic lesions on trunk and limbs during this time.

[figure not shown]
Twice weekly maintenance treatment will continue unchanged on areas that have not relapsed.

The subject will be examined at the next regular 4-week visit, but even if ‘clear’/‘almost clear’ at the regular visit, rescue treatment will continue. A relapse follow-up visit will take place at a relapse follow-up visit 4 weeks after the unscheduled visit where relapse treatment was initiated. If the subject is ‘clear’ or ‘almost clear’ according to PGA at this relapse follow-up visit, maintenance treatment on those areas will be resumed and the subject will follow the planned visit schedule.

If the subject is not ‘clear’ or ‘almost clear’ according to PGA after 4 weeks of relapse treatment, they will exit the trial. For illustration, see [Figure 3](#) below.

Figure 3 Relapse between regular 4-week (scheduled) visits – more than one week prior to the next regular visit

[figure not shown]

6.1.4.3 Relapse between regular 4 week (scheduled) visits – less than one week to the next regular visit

If a relapse/exacerbation of psoriasis occurs within one week (7 days) prior to the next scheduled visit, the subject should attend the next scheduled visit and the procedure described in section 6.1.4.1 should be followed. For illustration, see [Figure 4](#) below.

Figure 4 Relapse between regular 4 week (scheduled) visits – less than one week to the next regular visit

Trial visits (initial open-label treatment phase and maintenance phase)

The total trial duration will be up to 64 weeks (including 8 weeks follow-up) and will include at least 15 regular visits.

All post-randomisation visits (Visits 3 to 15) should be performed within \pm 4 days of the scheduled time relative to Visit 2; if the visit is performed outside of the visit window, the investigator should record the reason in the subject's medical record. The same visit window (\pm 4 days) is applicable for the follow-up of any unscheduled visits due to relapse.

The maintenance IP will be dispensed at each regular visit (from Visit 1 to Visit 14) and used maintenance IP will be collected at the next regular visit (from Visit 2 to Visit 15). Rescue IP will either be dispensed at a regular visit and collected at the next regular visit, or be dispensed at an unscheduled visit and collected at a relapse follow-up visit 4 weeks later, as applicable. The number of cans to be dispensed depending on the different trial phases is specified in section 10.4. Subjects should not discontinue treatment themselves between the trial visits. This applies to both maintenance treatment and rescue treatment following relapse.

The DLQI and EQ-5D-5L-PSO questionnaires will be completed at each visit to the site.

In addition, the subjects will be asked to complete the WPAI:PSO at baseline (Visit 1), at randomisation (Visit 2/Week 4), after approximately 6 months (Visit 8/Week 28) and at the end of treatment (Visit 15/Week 56).

At baseline (Visit 1), subjects will be instructed on how to capture psoriasis symptoms in the eDiary (e.g. erythema, scaliness, itching, etc...) using the PSI.

At home, subjects will complete the PSI daily during the open-label treatment phase (starting at Visit 1), then weekly during the first 28 weeks of the maintenance phase (Weeks 4 to 28) and the 2 last weeks of the maintenance phase (Week 54 to 56 - only applicable for completers).

The eDiary will also be used to record adherence to the once daily treatment regimen during the initial open-label treatment phase as well as the twice weekly and once-daily treatment regimens during the maintenance phase and relapse.

6.1.5 Follow-up Phase

There are three types of follow-up visits, here listed in chronological order:

Follow-up Visit 1 (FU1):

A follow up visit 1 is only relevant for subjects with an ongoing AE at end of treatment. A follow-up visit/contact (FU1) should be conducted 14 (\pm 2) days after the last on-treatment visit (Visit 15/Early Withdrawal), unless the final outcome of the event, as defined below, has been determined before then.

This follow-up visit/contact (FU1) will take place only if:

1. there is an on-going SAE at the last on-treatment visit.
2. there is an on-going non-serious AE at the last on-treatment visit which is classified as possibly or probably related to the IPs
3. the albumin-corrected serum calcium is above the reference range at the last on-treatment visit
4. the calcium:creatinine ratio is above the reference range and clinically significant at the last on-treatment visit

Where the (sub)investigator considers it appropriate, the Follow-up Visit may be performed as a telephone contact. If a subject also is eligible for a follow up visit 2 (FU2), the follow-up on the ongoing AE can wait until FU2 (see below).

Follow-up Visit 2 (FU2):

For subjects undergoing the adrenocorticotropic hormone (ACTH) challenge test, a follow-up visit (Visit FU2) will take place 28 days after the ACTH challenge test performed at the end of treatment (Visit 15/Early Withdrawal) if the end of treatment test shows a serum cortisol concentration ≤ 18 mcg/dl at both 30 minutes and 60 minutes after ACTH challenge (39, 40).

If the results of the ACTH challenge test at Visit FU2 continue to show a serum cortisol concentration ≤ 18 mcg/dl at both 30 minutes and 60 minutes after ACTH challenge, further ACTH challenge tests should be performed, but not more often than at 4-weekly intervals, until the adrenal suppression resolves (i.e. serum cortisol concentration > 18 mcg/dl at 30 minutes or at 60 minutes after the ACTH-challenge, or at both time-points).

Refer to Section 8.12.1 for further details on the ACTH challenge test.

Follow-up visits should be performed within ± 4 days of the scheduled time; if they are outside this window, the (sub)investigator should record the reason in the subject's medical record but LEO do not need to be notified.

Follow-up Visit 3 (FU3):

All subjects should be followed up for events of rebound for 8 weeks after last application of IP. The different scenarios are outlined below:

- Subjects who do not use rescue medication at Visit 15 will have a final contact (FU3) 8 weeks after Visit 15. Relapses confirmed at Visit 15 will be treated at the investigator's discretion; treatment with Enstilar[®] or IP is not allowed.
- Subjects who have completed 4 weeks of rescue treatment at Visit 15 (that is, Visit 15 is a relapse follow-up visit, see section 6.1.4.1) will have a final contact (FU3) 8 weeks after Visit 15.
- For subjects who use rescue medication at Visit 15 (that is, rescue medication was dispensed at an unscheduled visit after Visit 14 [see section 6.1.4.2]), the 8-week follow-up period will start after completion of the 4-week rescue treatment regimen (that is, at the relapse follow-up visit).

- Subjects who withdraw early from the trial, including subjects who leave the trial after the initial 4 weeks open-label treatment, will also have a follow-up visit (FU3) 8 weeks after their last IP application.

Subjects who experience rebound during the follow-up period prior to the FU3 visit will contact the site as soon as possible for an unscheduled follow-up visit (see below).

If the subject has not experienced a worsening of their psoriasis during the 8-week follow-up period, the FU3 contact may be conducted as a telephone contact, at the discretion of the investigator. If rebound is confirmed at the FU3 visit, the subject will be followed up for 14 days or until resolution (whichever occurs first). If the rebound is considered an SAE, the event must be followed up until a final outcome has been established, i.e. the follow-up may continue beyond the end of the clinical trial (see section [9.5](#)).

Rebound events in the follow-up period will be reported as (S)AEs in accordance with sections [9.2](#) and [9.4.1](#). See section [9.5](#) for the follow-up of related AEs during and after the trial.

Unscheduled follow-up visit

At the last treatment visit (Visit 15/Early Withdrawal), subjects should be instructed to contact the site if they experience a worsening of their psoriasis within the following 8 weeks to schedule a follow-up visit ('unscheduled follow-up'). The unscheduled follow-up visit should take place no more than 7 days after the initial contact.

If a relapse or rebound is confirmed at an unscheduled follow-up visit, the subject will be treated at investigator's discretion according to clinical practice. Note that relapse or rebound should not be treated with trial medication or Enstilar® during the follow-up period. The subject may come back to the trial site for another unscheduled follow-up visit, at the investigator's discretion. The subject will continue in the follow-up phase until the FU3 visit. If the subject experiences another worsening of their psoriasis within the 8-weeks follow-up period, they will contact the site again for a new unscheduled follow-up visit.

6.2 Sample Size

A total of 380 subjects should be randomised in the trial in order to have power for the primary maintenance treatment objective. In order to achieve 380 randomised subjects it is estimated that 832 subjects should be included in the trial.

The total number of subjects treated in the trial should also be sufficient to comply with ICH E1 regarding long-term safety. The aim is to achieve at least 300 subjects with 26 weeks of exposure and at least 100 subjects with 52 weeks of exposure.

For the HPA axis test, the aim is to achieve approximately 25 subjects undergoing HPA axis testing after 52 weeks of exposure.

The total number of randomised subjects can exceed 380 in order to achieve a sufficient number of subjects for long-term evaluation of safety and HPA testing.

The statistical power considerations for this sample size are described in section 11.1.

6.3 Randomisation

Subjects will be randomised in a 1:1 ratio to receive LEO 90100 or vehicle twice weekly during the maintenance phase. Randomisation will be stratified by trial site, HPA axis testing, and by baseline disease severity (mild, moderate, severe).

6.4 Blinding

During the open-label treatment phases (initial and relapse treatment), all subjects will receive LEO 90100.

During the maintenance phase, this trial is double-blind. Therefore, the packaging and labelling of the IPs must contain no evidence of their identity. It is not considered possible to differentiate between the IPs solely by sensory evaluation. No effects of the IPs which would reveal the identity of the individual treatment allocations are expected. Consequently, it is expected that the subjects and the site staff remain unaware of the individual treatment assignment during the conduct of the clinical trial.

7 Trial Population and Withdrawal

7.1 Subject Eligibility

The (sub)investigator should only enrol subjects, who meet all eligibility criteria, are not put at undue risk by participating in the trial, and can be expected to comply with the protocol.

The subject's eligibility for the clinical trial must be checked according to the inclusion and exclusion criteria at visits specified in "Schedule of Trial Procedures" [cf. 8.1].

Any implementation of national requirements/law for the subject's participation in the clinical trial must be ensured and described in the submission documentation to authorities/ethics committees, as applicable.

7.2 Inclusion Criteria

1. Signed and dated informed consent obtained prior to any trial related activities (including washout period)
2. Age 18 years or above
3. A clinical diagnosis of psoriasis vulgaris for at least 6 months involving the trunk and/or limbs, amenable to treatment with maximum of 100 g of trial medication per week
4. Psoriasis vulgaris on the trunk and/or limbs (excluding psoriasis on the genitals and skin folds) involving 2-30% of the body surface area (BSA)
5. A Physician's Global Assessment of disease severity (PGA) of at least 'mild' on trunk and limbs at Visit 1
6. A m-PASI score of at least 2 at Visit 1
7. A target lesion/target location of at least 3 cm at its longest axis located on the body (i.e., not on the scalp, face or intertriginous areas), scoring at least 1 ('mild') for each of redness, thickness and scaliness, and at least 4 in total by the Investigator's Assessment of Severity of the Target Lesion/Location
8. Females of child-bearing potential must have a negative urine pregnancy test at Visit 1
9. Females of child-bearing potential must agree to use a highly effective method of birth control during the trial*
10. Able to communicate with the investigator and understand and comply with the requirements of the trial

*A highly effective method of birth control is defined as one which results in a low failure rate (less than 1% per year) such as implants, injectables, combined oral contraceptives, some intra-uterine devices, sexual abstinence or vasectomised partner. The subjects must have used the contraceptive method continuously for at least 1 month prior to the pregnancy test, and must continue using the contraceptive method for at least 1 week after the last application of trial medication. A female is defined as not of child-bearing potential if she is postmenopausal (12 months with no menses without an alternative medical cause), or surgically sterile (hysterectomy or bilateral ovariectomy).

Additional inclusion criteria for subjects undergoing HPA axis test (assigned sites only):

11. Signed and dated informed consent obtained for having ACTH challenge tests performed
12. An extent of psoriasis vulgaris on trunk and/or limbs of disease severity (PGA) of at least 'moderate' affecting between 10 and 30% of the body surface area (BSA) excluding psoriatic lesions of genitals and skin folds at Visit 1
13. At Visit 1, a normal HPA axis function including a serum cortisol concentration above 5 mcg/dl before ACTH-challenge and above 18 mcg/dl 30 minutes after ACTH-challenge.

7.3 Exclusion Criteria

1. Systemic treatment with biological therapies, whether marketed or not, with a possible effect on psoriasis vulgaris within the following time periods prior to Visit 1:
 - etanercept – within 4 weeks prior to Visit 1
 - adalimumab, infliximab – within 8 weeks prior to Visit 1
 - ustekinumab – within 16 weeks prior to Visit 1
 - secukinumab – within 12 weeks prior to Visit 1
 - other products – within 4 weeks/5 half-lives prior to Visit 1 (whichever is longer)
2. Systemic treatment with all other therapies with a possible effect on psoriasis vulgaris (e.g. corticosteroids, retinoids, methotrexate, ciclosporin and other immunosuppressants) within 4 weeks prior to Visit 1
3. Systemic treatment with apremilast within 4 weeks prior to Visit 1
4. Subjects who have received treatment with any non-marketed drug substance (i.e. a drug which has not yet been made available for clinical use following registration) within 4 weeks/5 half-lives (whichever is longer) prior to Visit 1
5. Psoralen combined with Ultraviolet A (PUVA) therapy within 4 weeks prior to Visit 1
6. Ultraviolet B (UVB) therapy within 2 weeks prior to Visit 1
7. Topical anti-psoriatic treatment on the trunk and/or limbs (except for emollients) within 2 weeks prior to Visit 1
8. Topical treatment on the face, scalp and skin folds with corticosteroids, or vitamin D analogues within 2 weeks prior to Visit 1

9. Severe and/or extensive scalp psoriasis which, in the opinion of the investigator, requires treatment with potent or super-potent corticosteroids which will be prohibited during the trial
10. Pre-existing overt atrophy or teleangiectasia in treatment areas
11. Planned initiation of, or changes to, concomitant medication that could affect psoriasis vulgaris (e.g. beta blockers, antimalarial drugs, lithium, ACE inhibitors) during the trial
12. Current diagnosis of guttate, erythrodermic, exfoliative or pustular psoriasis
13. Subjects with any of the following conditions present on the treatment area: viral (e.g. herpes or varicella) lesions of the skin, fungal and bacterial skin infections, parasitic infections, skin manifestations in relation to syphilis or tuberculosis, acne vulgaris, atrophic skin, striae atrophicae, fragility of skin veins, ichthyosis, ulcers and wounds
14. Other inflammatory skin disorders (e.g. seborrhoeic dermatitis or contact dermatitis) on the treatment area that may confound the evaluation of psoriasis
15. Planned excessive exposure of area(s) to be treated with trial medication to either natural or artificial sunlight (including tanning booths, sun lamps etc.) during the trial
16. Known or suspected disorders of calcium metabolism associated with hypercalcaemia
17. Known or suspected hypersensitivity to component(s) of investigational products
18. Current participation in any other interventional clinical trial
19. Previously screened in this trial
20. In the opinion of the (sub)investigator, the subject is unlikely to comply with the clinical trial protocol (e.g. due to alcoholism, drug addiction or psychotic state)
21. Females who are pregnant, wishing to become pregnant during the trial or are breastfeeding
22. Subjects in close affiliation with the trial personnel (e.g. immediate family member or subordinate), subjects being a member of the clinical trial personnel, or being an employee of the sponsor or a contract research organization (CRO) involved in the trial
23. Subjects who are institutionalized by court order or by local authority.

Additional exclusion criteria for subjects undergoing HPA axis test (assigned sites only):

24. A history of allergic asthma, serious allergy or serious allergic skin rash

25. Known or suspected hypersensitivity to component(s) of CORTROSYN® (including cosyntropin/tetracosactide) (in the US) / Synacthen® (including tetracosactide) (in Europe)
26. The use of inhaled corticosteroids in the 4 weeks prior to Visit 1 or during the trial
27. Systemic corticosteroid treatment in the 12 weeks prior to Visit 1 or during the trial
28. Enzymatic inductors (e.g., barbiturates, phenytoin, rifampicin) within 4 weeks prior to Visit 1 or during the trial
29. Systemic or topical cytochrome P450 inhibitors (e.g., ketoconazole, itraconazole, metronidazole) within 4 weeks prior to Visit 1 or during the trial. Topical ketoconazole within 2 weeks prior to Visit 1
30. Hypoglycemic sulfonamides within 4 weeks prior to Visit 1 or during the trial
31. Antidepressive medications within 4 weeks prior to Visit 1 or during the trial.
Oestrogen therapy (including contraceptives), antidepressant medications and any other medication known to affect cortisol levels or HPA axis integrity within 4 weeks prior to baseline
32. Not following nocturnal sleep patterns
33. Any of the following conditions, whether known or suspected:
 - depression and endocrine disorders (e.g. Cushing's disease, Addison's disease, diabetes mellitus) known to affect cortisol levels or HPA axis integrity
 - cardiac disorders associated with abnormal QT intervals or rhythm disturbances including clinically significant bradycardia or tachycardia
 - severe renal insufficiency
 - severe hepatic disorders.

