10.9 CORTROSYN® (cosyntropin) / Synacthen® (tetracosactid) for Injection

CORTROSYN® (used in the US) is a commercial solution for injection containing cosyntropin that will be used for the ACTH-challenge test. One ampoule contains cosyntropin PhEur 250 micrograms (equivalent to 25 IU ACTH).

Synacthen® (used in Europe) is a commercial solution for injection containing tetracosactidhexaacetate that will be used for the ACTH challenge test. One ampoule contains 1 ml of 0.28 mg tetracosactid-hexaacetate (0.25 mg tetracosactid which equals 25 IU ACTH).

CORTROSYN® / Synacthen® is a non-Investigational Medicinal Product. The applicable product will be sourced by the trial sites, except in Poland. In Poland Synacthen® will be supplied by the sponsor.

CORTROSYN® will be used in accordance with the U.S. Prescribing Information for the marketed product (see [Appendix 2: U.S. Prescribing information for CORTROSYN® \(cosyntropin\) for injection](#)). Synacthen® will be used in accordance with the SmPC (see [Appendix 3: Summary of Product Characteristics for Synacthen® \(Tetracosactide\) Ampoules 250mcg](#))

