10.9.1.4 Precautions

Product specific precautions and handling instructions will be provided in the product monograph specific to the chosen product.

General precautions for use with 0.9% Sodium Chloride Injection, USP (in connection to reconstitution of CORTROSYN® (in the US)) include:

- Do not use unless the solution is clear and seal intact.
- Do not re-use containers.
- Discard unused portion.

See the Prescribing Information for CORTROSYN® in [Appendix 2: U.S. Prescribing information for CORTROSYN® \(cosyntropin\) for injection](#) and for Synacthen® in [Appendix 3: Summary of Product Characteristics for Synacthen® \(Tetracosactide\) Ampoules 250mcg](#) for further details.

Athletes should be aware that CORTROSYN® and Synacthen® contain active ingredients that may cause a positive result on doping tests.

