4.3 Contraindications

Known hypersensitivity to tetracosactide and/or ACTH or to any of the excipients listed in section 6.1 List of excipients.

Synacthen is contra-indicated in patients with allergic disorders (e.g. asthma) (see Section 4.4 Special warnings and precautions for use), acute psychosis, infectious diseases, peptic ulcer, refractory heart failure, Cushing's syndrome, treatment of primary adrenocortical insufficiency and adrenocongenital syndrome.

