4.4 Special warnings and precautions for use

Before using Synacthen, the doctor should make every effort to find out whether the patient is suffering from, or has a history of, allergic disorders (see Section 4.3 "Contra-indications"). In particular, he should enquire whether the patient has previously experienced adverse reactions to ACTH, Synacthen or other drugs.

Synacthen should only be administered under the supervision of appropriate senior hospital medical staff (e.g. consultants).

If local or systemic hypersensitivity reactions occur after the injection (for example, marked redness and pain at the injection site, urticaria, pruritus, flushing, faintness, severe malaise or dyspnoea), Synacthen or other ACTH preparations must be discontinued and should be avoided in the future. Hypersensitivity reactions tend to occur within 30 minutes of an injection. The patient should therefore be kept under observation during this time.

Preparation should be made in advance to combat any anaphylactic reaction that may occur after an injection of Synacthen. In the event of a serious anaphylactic reaction, the patient should be treated appropriately with adrenaline and steroids.

Synacthen Ampoules should not be used in the presence of active infectious or systemic diseases, when the use of live vaccine is contemplated or in the presence of a reduced immune response, unless adequate disease specific therapy is being given.

Use with care in patients with hypertension and thromboembolic tendencies.

Use cautiously in patients with ocular herpes simplex owing to possible

corneal perforation.

The increased production of adrenal steroids may result in corticosteroid type effects:

- Psychological disturbances may be triggered (e.g. euphoria, insomnia, mood swings, personality changes and severe depression, or even frank psychotic manifestations). Existing emotional instability or psychotic tendencies may be aggravated
- Latent infections (e.g. amoebiasis, tuberculosis) may become activated
- Ocular effects may be produced (e.g. glaucoma, cataracts)
- Dosage adjustments may be necessary in patients being treated for diabetes or hypertension
- If Synacthen is used in any of the following conditions, the risks of treatment should be weighed against the possible benefits: ulcerative colitis, diverticulitis, recent intestinal anastomosis, kidney failure, hypertension, predisposition to thromboembolism, osteoporosis, myasthenia gravis.

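### At sites using Synacthen, the numbered HPA exclusions are narrower than the SmPC contraindications the protocol makes binding: allergic disorders are only partly covered, and peptic ulcer and refractory heart failure are missing

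*Protocol*

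**What the plan says.** Protocol section 7.3 adds exclusions 24 to 33 for subjects having the HPA axis test. No. 24 is "A history of allergic asthma, serious allergy or serious allergic skin rash". No. 25 covers hypersensitivity to components of the test product. No. 33 covers depression and endocrine disorders, severe renal and severe hepatic disease, and, on the cardiac side, "cardiac disorders associated with abnormal QT intervals or rhythm disturbances including clinically significant bradycardia or tachycardia".

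Section 10.9 states that Synacthen "will be used in accordance with the SmPC" in Appendix 3. It also states: "In Poland Synacthen® will be supplied by the sponsor". Section 10.9.1.4 adds: "Product specific precautions and handling instructions will be provided in the product monograph specific to the chosen product".

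In Appendix 3, SmPC section 4.3 says "Synacthen is contra-indicated in patients with allergic disorders (e.g. asthma") and continues with "acute psychosis, infectious diseases, peptic ulcer, refractory heart failure" and some endocrine conditions. SmPC section 4.4 requires an enquiry when the product is given: "Before using Synacthen, the doctor should make every effort to find out whether the patient is suffering from, or has a history of, allergic disorders".

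Protocol section 8.12.1 schedules the test at Visits 1, 2, 8 and 15 (or early withdrawal), with FU2 and further tests if suppression persists. It lists what must be done before each test (vital signs, blood and urine samples, biomarker sample, pregnancy test) and says the injection is given as section 10.9 describes. Table 4 places the inclusion/exclusion check at screening and Visit 1.

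**The concern.** A site that works through the numbered criteria can find a subject eligible for the ACTH test and then be told by section 10.9, through Appendix 3, that the same subject should not be injected. The specific list and the general clause give different answers, and the specific list is the one used at enrolment.

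The injection is diagnostic and brings the subject no therapeutic benefit, so tolerance for avoidable risk is low. The allergy item matters most. SmPC 4.8 warns that hypersensitivity reactions tend to be more severe, up to anaphylactic shock, in people prone to allergy and especially those with asthma.

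**Working it through.** No figure in the plan bears on this point, so the check is a comparison of texts. Each SmPC 4.3 item is set against the criteria that apply to the HPA subset.

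| SmPC 4.3 item | Protocol criteria | Result |
|---|---|---|
| Hypersensitivity to the product | No. 25 | Covered |
| Allergic disorders, asthma as example | No. 24: allergic asthma, or allergy or rash qualified as serious | Narrower |
| Peptic ulcer | None | Absent |
| Refractory heart failure | No. 33 cardiac item: QT and rhythm only | Absent |
| Infectious diseases | No. 13, on the treatment area only | Partly covered; not pressed, because SmPC 4.4 allows use under adequate disease-specific therapy |
| Acute psychosis | Inclusion 10 and exclusion 20, indirectly | Not counted as a gap |
| Cushing's syndrome, primary adrenal insufficiency, adrenogenital-type disorder | No. 33 endocrine item and inclusion 13 (normal HPA function) | Covered in substance |

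**The allergy gap.** Non-serious allergic disease is clearly left in. Asthma not classed as allergic is also left in by no. 24. No. 26 and Table 2 would remove some of those subjects by barring inhaled corticosteroids in the four weeks before Visit 1 and during the trial. Section 7.8.2 pulls the other way: it allows inhaled steroids except in the four weeks before an ACTH challenge for this subset. No. 26 therefore cannot be relied on to close the asthma gap.

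**Repeat tests.** Section 8.12.1 sends every injection to section 10.9, with no limit to Visit 1. Section 10.9 requires use under the SmPC, and SmPC 4.3 and 4.4 apply whenever Synacthen is used. The obligation therefore holds at all 4 scheduled tests and at any later ones. What is missing is an explicit line in the pre-test list.

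**A possible origin (inference).** The CORTROSYN label in Appendix 2 names a previous adverse reaction as its only contraindication, so no. 24 is stricter than that label needs. In Appendix 12, the HPA exclusion that Amendment 1 shows as reworded to name Synacthen is no. 25. Nos. 24 and 33 are not shown as changed. This fits a list written with CORTROSYN in mind and not fully re-checked against the European label.

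**Size.** The aim is about 25 subjects tested after 52 weeks of exposure, across all countries. The documents give neither the Synacthen share nor the frequency of the uncovered conditions, so no count of affected subjects can be derived.

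**The case against.** The strongest reply is that the safeguard is already in the protocol. The SmPC is reproduced in full, section 10.9 makes it binding, section 10.9.1.4 points to it again, and SmPC 4.4 adds senior supervision, observation after the injection and readiness to treat anaphylaxis. Section 7.1 also tells investigators not to enrol anyone put at undue risk. A site that injected a contraindicated subject would be in breach. On this view, repeating label contraindications as numbered criteria is only a drafting preference. Polish sites, which the sponsor supplies, have the contraindication list in Appendix 3 like everyone else.

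Much of this stands, and it is why the point is minor. It does not remove the conflict: a numbered eligibility rule that is looser than the binding label invites the wrong answer at enrolment.

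Other parts of the reply also stand:

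- Asthma appears in SmPC 4.3 as an example of an allergic disorder, so whether non-allergic asthma is meant is debatable. The firm gap is non-serious allergy.
- No. 24 reaches back to any history, which is wider in time than the wording of 4.3.
- No. 33 goes beyond 4.3 on rhythm, renal and hepatic disease.
- Peptic ulcer and heart failure carry little risk here, because SmPC 4.8 treats the corresponding steroid-type effects as unlikely with short diagnostic use.

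A reader might infer that the tests after Visit 1 go ahead with no contraindication check. The documents do not support that. The obligation carries by reference, as shown above. Table 4 also records adverse events and concomitant medication at each test visit, and section 8.6 makes any new illness from Visit 1 onward reportable.

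**Conclusion.** The point holds as a minor safety-consistency correction. At sites using Synacthen, one SmPC 4.3 item is narrowed in the HPA exclusions (allergic disorders) and two are absent (peptic ulcer, refractory heart failure). The criteria therefore admit subjects whom Appendix 3 contraindicates. The allergy item carries nearly all the clinical weight.

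The conclusion assumes that sites apply the numbered list as the working eligibility test. It does not assume that anyone ignores the SmPC. The number of subjects affected is unknown. A reader might be tempted to size the problem by projecting the total number of ACTH injections from the trial's planning rates. That total would include US sites using CORTROSYN, whose label has no such contraindications, so it would not measure this issue.

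Nothing here touches the efficacy endpoints, power or type I error.

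**What to change.** For Synacthen sites only:

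1. Reword no. 24 to follow the SmPC: allergic disorders, with asthma as the example, without the seriousness qualifier.
2. Add peptic ulcer and refractory heart failure to no. 33.
3. Optionally, add one line to the pre-test list in 8.12.1: before each ACTH test, including FU2 and repeats, confirm that no contraindication in Appendix 3 sections 4.3 and 4.4 is present.

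The cost is two criteria edits and, if wanted, one procedural line. The wider no. 24 would exclude some people with mild allergy, so slightly fewer European subjects would enter a subset whose recruitment difficulty is recorded under Amendment 4 in Appendix 12. Because nos. 24 to 33 apply only to the HPA test, those subjects could still join the main trial.
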